Sample Size: Sample size calculation was based on the hypotheses associated with the Effectiveness component of RE-AIM and our prior research.^{8,10,12,22,23,29,77} With regard to facility level outcomes, our prior work resulted in effect sizes of 0.9 for environmental and policy changes.^{22,76,120} With the proposed sample size of 50 facilities, the statistical power for these two measures will be adequate (>.90 for both outcomes based on our analysis plan). For resident level outcomes, person-centered approaches resulted in a small intervention effect (Cohen's $d=0.19$) to maintain or improve BPSD, function, wellbeing or experiencing adverse events.^{8,10,12,22,23,29,77} Given a two-tailed alpha of 0.05, an estimated intra-class correlation coefficient (ICC) between clusters (facilities) of 0.02, a correlation coefficient between repeated measures (baseline, 4 and 12 months) of 0.6, and assuming even dispersion of means, a total sample of 500 residents will provide sufficient power ($\geq .80$) to detect the small effect size for group differences.¹²¹ Our prior research showed a 20% rate of attrition over 12 months.^{8,77} Therefore, we anticipate that a total of 625 residents from 50 nursing homes will be sufficient to demonstrate outcomes. To achieve this sample we will recruit 12-13 residents in each facility.

Setting: Nursing homes will be invited and eligible to participate if they: (a) agree to actively partner with the research team to change practice; (b) have at least 100 beds; (c) identify a RN, LPN or CNA to be the Champion; and (d) are able to access email and websites via a phone, tablet or computer. Recruitment of facilities will be done by mailing invitations to eligible facilities within the two states followed by telephone calls. We will also post invitations on relevant websites (see letters of support). This approach has been used successfully in our prior work.²² Fifty percent of the facilities we invited participated.²² Currently there are 152 nursing homes of appropriate size in Maryland and 439 in Pennsylvania. Given the regulatory climate with respect to dementia care in nursing homes, we are confident we will be able to engage 25 facilities per state.

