Once the nursing facility expresses an interest in participating in the study, the facility will be randomized to one of three cohort groups and then randomized to EIT-4-BPSD or EO. We will implement EIT-4-BPSD in 8-10 facilities and the EO intervention in 8-10 facilities during each cohort period. We recognize there will be a period of time between recruitment and implementation of study related activities and will keep facilities updated. In addition, we will maintain a waiting list of interested facilities in the event that some volunteer facilities decide not to participate (their data will be included in terms of Reach).

Resident Participants: We will keep our resident enrollment criteria to a minimum to increase external validity. Residents will be eligible to participate if they: (a) are living in a participating nursing home; (b) are 55 years of age or older; (c) have a history within the past month of exhibiting at least one BPSD; (d) have cognitive impairment as determined by a score of 0-12 on the Brief Interview of Mental Status (BIMS);¹²² (e) are not enrolled in Hospice; and (f) are not in the nursing facility for short-stay rehabilitation care. We will obtain a list of all eligible residents from a designated staff member and randomly approach each resident until 12-13 residents per facility are recruited by research assistants (RAs) (N= 625 residents). This sampling approach is used to assure variability and equal participation from each nursing facility in the study. Based on our prior research and recent data from the most recent Nursing Home Compendium¹²³ we conservatively anticipate that 25% to 30% of residents will be eligible.^{123,124} We are confident we will be able to recruit 12-13 residents per facility.^{8,77,125} See the Human Subjects section for details of the consenting and recruitment process.

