Behavioral Symptoms (Effectiveness): Depressive symptoms will be measured using the *Cornell Scale for Depression in Dementia (CSDD)*^{139,140}. CSDD is a 19 item survey that assesses depressive symptoms in individuals with dementia. There is evidence of reliability and validity of the CSDD.¹³⁹⁻¹⁴¹ Aggressive and/or resistive behaviors during care activities will be measured using the *Resistiveness to Care Scale*,¹⁴² a reliable and valid 13 item Likert scale that assesses residents' behaviors during activities of daily living. Agitated

behaviors will be measured using the *Cohen-Mansfield Agitation Inventory (CMAI)*,^{143,144} a survey of disturbing behaviors commonly found in residents with dementia. The 14 item version CMAI uses a 5-point Likert scale to rate the frequency of behavioral symptoms.^{144,145} Prior use supported evidence of reliability and validity.^{144,145}

Function (Effectiveness): *The Barthel Index (BI)*¹⁴⁶ is a 10 item measure of performance of activities of daily living with evidence of internal consistency, inter-rater reliability and validity.^{146 147} Items are weighted to account for the amount of assistance required. A total score of 100 indicates complete independence.

Quality of Life: will be measured using the *Quality of Life-AD (QoL-AD)*¹⁴⁸ scale. The QoL-AD is a 13 item reliable and valid instrument designed to rate the resident's quality of life from the staff perspective. Examples of items include physical condition, mood, relationships and participation in meaningful activities. Ratings are obtained on a 4 point scale (1= poor to 4=excellent) and total scores range from 13-52.¹⁴⁸

Adverse Events (Effectiveness): will be based on data obtained from medical records and designated individuals within the facilities (e.g., quality assurance nurse). Adverse events will include falls and transfers to hospitals or emergency rooms and physical restraint use. Baseline will include the four months prior to treatment implementation; 4 month will include those between baseline and 4 months; and 12 month those that occur between 4 months and 12 months post implementation of the intervention. Restraint use will be based on the reliable Minimum Data Base 3.0 definition of assessment for use of restraints.¹⁴⁹⁻¹⁵¹

Data Analysis:

Aim 1: To implement and test the implementation of EIT-4-BPSD.

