Descriptive statistics including measures of central tendency, dispersion and appropriate visualization approaches (e.g., box plots and spaghetti plots) will be performed on each outcome variable for residents and facilities. This will be done to ascertain distributional characteristics and ensure that the assumptions (e.g., normality) associated with the planned statistical procedures are met. When necessary, transformations will be performed. All analyses will be done using an intent-to-treat philosophy. Baseline characteristics (both resident level and facility level) will be compared between intervention and control groups and the relevant variables (e.g., age) that differ by group will be included as covariates in hypotheses testing. In particular we will utilize constructs known to correlate with BPSD including gender, pain, health status and cognitive and functional impairment. Linear mixed models (LMMs)¹⁵³ for longitudinal data (baseline, 4 and 12 months) will be used to assess the intervention effect on continuous outcomes (i.e., function, behavioral symptoms, and quality of life) accounting for clustering of residents that may occur within the same facility and correlations between repeated measurements of each resident. Mixed-effect Poisson regression [i.e., Generalized Linear Mixed Model

(GLMM)] will be conducted to assess the effect of the intervention on count outcomes (i.e., number of adverse events including number of falls, hospitalizations and emergency room visits, restraint use). The fixed effects included in the models will be treatment group (EIT-4-BPSD versus EO), time (baseline, 4 and 12 months), group-by-time interaction term and the aforementioned relevant covariates (e.g., age). Random effects will include facilities and residents.

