The hypothesis will be tested by evaluating the interaction term for each outcome variable. Similar LMMs will be used to compare changes in facility level measures (i.e., environments, policies) from baseline to 12 months with only facility included as random effects. For each hypothesis, exploratory analyses will be performed to assess model assumptions. Post-analysis diagnostic measures (e.g., residuals) will be explored to assess model fit. All tests will use a 5% significance level. The use of LMM will provide flexibility with regard to assumptions related to the covariance structure of the residuals and the presence of missing data for the repeated measures.¹⁵⁴ Missing data. In prior research we had 20% rate of attrition at the resident level and 10% of facilities.^{22,23} If there is significant dropout, we will identify baseline characteristics that differ between persons or facilities that drop out. Maximum likelihood methods will be used for primary analyses, which address non-informative dropout (missing at random [MAR]). If "informative" dropout appears possible, we will consider sensitivity analyses that involve adding these relevant baseline covariates to make the MAR assumption more plausible.¹⁵⁵ Qualitative data will be collected to inform effectiveness outcomes.

Adoption: Staff Adoption: Descriptive statistics will be done to evaluate the number of Internal Champions and Stakeholder team members participating in initial face-to-face training and monthly meetings among the 25 facilities randomized to EIT-4-BPSD. We will also consider improvement in scores on the Use of Behavioral Interventions for BPSD measure at each testing time point as evidence of adoption among staff. Facility Adoption: Facility adoption will be based on changes in environments, policies, and care plans of residents at 4 and 12 months post implementation of EIT-4-BPSD such that there is at least 1 item changed in each assessment area. Further we will describe differences among EIT-4-BPSD facilities that demonstrate adoption (based on changes in environments, policies and care plans) early (the first 4 months) versus late adopters (between 5-12 months) versus those that are non-adopters (no change by 12 months). Predictors such as facility characteristics will be compared across the three potential times of adoption (early, late, nonadopters).

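### The Poisson model for adverse-event counts has no time-at-risk offset and no rule for partly observed windows, so unequal resident loss between arms could distort the rate ratio

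*Combined protocol and SAP*

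**What the plan says.** The Adverse Events paragraph under Resident RE-AIM Measures takes falls, transfers to hospital or emergency room, and restraint use from medical records and designated facility staff. Baseline covers the four months before implementation and the 4-month count covers the time from baseline to month 4. The last count is "12 month those that occur between 4 months and 12 months post implementation of the intervention". Restraint use follows a Minimum Data Base 3.0 assessment definition.

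The Effectiveness part of Data Analysis assigns a mixed-effect Poisson regression to the "number of adverse events including number of falls, hospitalizations and emergency room visits, restraint use". It lists the model terms: "The fixed effects included in the models will be treatment group (EIT-4-BPSD versus EO), time (baseline, 4 and 12 months), group-by-time interaction term", plus covariates, and then "Random effects will include facilities and residents". For the test it says: "The hypothesis will be tested by evaluating the interaction term for each outcome variable". No offset, resident-days or other person-time denominator appears there or elsewhere in the text.

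On loss, the Sample Size section says: "Our prior research showed a 20% rate of attrition over 12 months". The Missing data text repeats the 20%, adds 10% of facilities, and plans maximum likelihood under missing at random. It does not say whether a resident who dies or leaves inside a window contributes a truncated count, a zero or a missing value. The only length-of-stay criterion under Resident Participants is "f) are not in the nursing facility for short-stay rehabilitation care"; no minimum prior stay is set.

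**The concern.** A Poisson model without an exposure term compares mean counts per record, not rates. A resident who leaves in month 6 has two of the eight months in the last window in which to be counted. If that count enters beside complete ones, lost observation time looks like absence of events. When one arm loses more residents than the other, the group-by-time term picks up the difference in observation time.

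Fewer adverse events in the EIT-4-BPSD arm is part of H1. If that arm lost more residents, the artefact would point towards the hypothesised benefit and could hide a true excess. If the education-only arm lost more, it would work against the intervention.

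**Working it through.** **1. The plan's own figure.** 500 evaluable residents / (1 − 0.20) = 625, as stated. The documents give no event rate, rate ratio or power for the adverse-event counts, and no attrition by arm, timing or reason. The sizes below therefore rest on assumptions.

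**2. What cancels.** The windows last 4, 4 and 12 − 4 = 8 months. Time is categorical, so window length multiplies the expected count equally in both arms and drops out of the interaction. A difference between arms in the *share* of a window observed does not drop out.

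**3. Share observed.** Let *a* be an arm's 12-month loss, and assume exit is uniform over 12 months. Then *a*/3 leave in months 0–4 and 2*a*/3 in months 4–12, each contributing on average half of the window in which they leave.

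- Months 0–4: 1 − *a*/6
- Months 4–12, everyone kept and residents gone before month 4 entered as zeros: (1 − *a*) + ½ × 2*a*/3 = 1 − 2*a*/3
- Months 4–12, only those present at month 4: (1 − 2*a*/3) / (1 − *a*/3)

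At *a* = 0.20 these are 0.967, 0.867 and 0.929.

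**4. Spurious 12-month rate ratio.** With the same true rate in both arms and a fully observed baseline, the ratio of expected counts is the ratio of observed shares.

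| Assumed loss | Present at month 4 | With zeros |
|---|---|---|
| 20% v 20% | 0.929/0.929 = 1.00 | 0.867/0.867 = 1.00 |
| 22.5% v 17.5% | 0.919/0.938 = 0.98 | 0.850/0.883 = 0.96 |
| 25% v 15% | 0.909/0.947 = 0.96 | 0.833/0.900 = 0.93 |
| 30% v 10% | 0.889/0.966 = 0.92 | 0.800/0.933 = 0.86 |

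For the 0–4 month window the four ratios are 1.00, 0.99, 0.98 and 0.97.

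**5. Effect on the test.** A simulation used 50 homes, 625 residents, a true rate ratio of 1 and 1,000 runs per setting. Assumed inputs were 0.10 or 0.25 events per resident-month, log-scale SDs of 0.2 between homes and 0.6 between residents, and non-informative exit. Poisson regression with facility-clustered standard errors stood in for the mixed model. Rejection of the 12-month interaction at nominal 5%, over the two event rates:

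| Loss | Truncated counts | With zeros | Offset | Partial windows missing |
|---|---|---|---|---|
| 20% v 20% | 5.4–6.3% | 6.7–7.3% | 5.2–6.9% | 4.7–6.2% |
| 25% v 15% | 7.1–8.0% | 9.7–15.2% | 6.0–6.2% | 5.2–6.6% |
| 30% v 10% | 10.1–14.4% | 19.8–33.6% | 6.0–6.2% | 4.8–6.5% |

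The mean rate ratio was 1.00 throughout with the offset, and 0.99–1.00 with partial windows missing.

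**6. Can a gap arise?** The plan's 10% facility loss is 5 of 50 homes. If five withdraw at random from 25 per arm, the chance of a 4:1 or more extreme split is 2 × [C(25,5) + C(25,4) × 25] / C(50,5) = 2 × (53,130 + 316,250) / 2,118,760 = 0.35. A 4:1 split is 16% v 4% of homes. This shows that chance alone can produce a gap in homes; it does not estimate the gap in residents.

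**The case against.** The best defence is that data are collected at baseline, 4 and 12 months, and maximum likelihood under missing at random is planned. A resident gone before a visit may simply be missing at that visit. On that reading the simulation shows almost no arm bias under non-informative exit. This stands as a possible reading, so a reader who infers that the plan treats leavers as fully observed goes further than the text.

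It does not close the gap. A count cut short is a recorded number over less time, and likelihood methods for missing values do not rescale it. Events come from records, so those before exit can be retrieved, and the intent-to-treat commitment favours keeping these residents. Setting the window to missing instead throws away falls and transfers that did occur.

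Other stronger readings are not supported:

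- *The arm losing more residents will look safer.* This needs unequal loss, and the documents give only one overall figure. The Maintenance section plans to compare facility attrition between arms, which makes a difference a recognised possibility but not an expected one.
- *The 4-, 4- and 8-month windows bias the comparison.* Categorical time absorbs them.
- *Recent admissions bias the comparison.* They shorten only the baseline window, and cancel from the group-by-time test unless more common in one arm.
- *The size is larger.* Putting all the loss in the 8-month window at half exposure gives 0.8875/0.9125 = 0.97, 0.875/0.925 = 0.95 and 0.85/0.95 = 0.89. Nothing in the documents places all the loss there.
- *These counts are the trial's safety evidence, and leavers are its frailest residents.* The plan labels the counts as effectiveness outcomes and gives no reasons for exit.

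**Conclusion.** The concern holds in a conditional form. The count model lacks an exposure term, and the handling of partial windows is unstated. Neither available reading is satisfactory: one risks bias and the other loses events. Any arm bias needs truncated or zero counts together with unequal loss. It is modest: about 2%, 4% and 8% on the 12-month rate ratio for gaps of 5, 10 and 20 points, or 4%, 7% and 14% with zeros. For a 10-point gap with truncated counts, the false-positive rate moves only from about 6% with the offset to 7–8% without it. These figures depend on uniform, non-informative exit and on the assumed loss splits; the rejection rates also depend on the assumed event rates and variances. The change is still worth making, because an offset is a better and inexpensive method for counts over unequal follow-up.

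**What to change.** In the Effectiveness analysis text:

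- Record, for each resident and window, the days resident in the facility and alive.
- Include every resident with any exposure in a window, and state how deaths, discharges and admissions within it are counted.
- Add log(days at risk) as an offset in the mixed models for falls and for hospital and emergency transfers.
- Report rates per 1,000 resident-days by arm and window.
- For restraint use, choose a denominator that matches its assessment-based definition, such as the number of assessments. Resident-days are not clearly right there.

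The cost is a few lines of text and the extraction of admission, discharge and death dates. The medical chart is already a data source, but the text does not say that these dates are collected, so the data forms need checking. An offset corrects for unequal observation time only; it does not correct exit that is itself related to event risk.

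### The select-if-different covariate rule adds almost nothing to the group-by-time test; separately, adjusting for the baseline outcome would cut the 12-month variance by about 17%

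*Combined protocol and SAP*

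**What the plan says.** In section C, Data Analysis, Effectiveness, baseline characteristics of residents and facilities are compared between arms, and "the relevant variables (e.g., age) that differ by group will be included as covariates in hypotheses testing". The next sentence says that constructs known to correlate with BPSD will be used, and names gender, pain, health status, cognition and function. It does not say whether these enter always or only when the arms differ on them, and no criterion for differing is given.

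The model is then set out: "The fixed effects included in the models will be treatment group (EIT-4-BPSD versus EO), time (baseline, 4 and 12 months), group-by-time interaction term", plus those covariates, with facility and resident random effects. Baseline is thus one of the response times. No covariate-by-time term is listed, and the baseline value of the outcome is not used for adjustment. On the test: "The hypothesis will be tested by evaluating the interaction term for each outcome variable".

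The Sample Size section gives a two-sided 5% level, d = 0.19, "an estimated intra-class correlation coefficient (ICC) between clusters (facilities) of 0.02" and "a correlation coefficient between repeated measures (baseline, 4 and 12 months) of 0.6". It states that "a total sample of 500 residents will provide sufficient power" of at least .80, and raises this to 625 enrolled for 20% attrition. It does not name the contrast or test behind the power figure.

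**The concern.** Two separate matters sit in this paragraph.

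The first is the covariate rule. Choosing covariates by observed group difference makes the model depend on the data, and on one reading it leaves out strong predictors that happen to be balanced. The reader is also led to expect that the adjustment does something for the H1 test. In a model that has baseline as a response and tests the group-by-time interaction, it does almost nothing.

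The second is the contrast. The group effect at baseline is free, so the 12-month interaction is in effect a comparison of change scores. At a correlation of 0.6, a change score is less precise than an analysis adjusted for the baseline value. With a small target effect (d = 0.19) and 25 facilities per arm, that precision is worth having, and the data for it are already collected.

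**Working it through.** **Inputs.** From Sample Size: two-sided alpha 0.05, d = 0.19, ICC 0.02, correlation 0.6, 500 evaluable residents, 50 facilities. Allocation is 25 facilities per arm (Adoption paragraph), so 10 evaluable residents per facility and 250 per arm. Assumed: total SD 1, random-intercept covariance (facility variance 0.02, resident 0.60 − 0.02 = 0.58, residual 1 − 0.60 = 0.40) and a normal approximation. Φ is the standard normal distribution function.

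**1. The plan's own figures.** 500 / (1 − 0.20) = 625, reproduced. The power figure depends on the contrast. For the mean of 4 and 12 months minus baseline, the variance of the between-arm difference is 2 × 0.40 × (1 + 1/2) / 250 = 0.0048 and the SE is 0.0693. Power is Φ(0.19/0.0693 − 1.96) = 0.78, within two points of .80. Other contrasts give less: 0.66 for the 12-month change, and 0.69 for the 2-df interaction if the effect is d at both visits.

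**2. Main-effect covariates and the interaction.** With complete data the 12-month interaction estimate is (arm 1 mean at 12 months − arm 1 mean at baseline) − (the same for arm 0). A term β·x that is constant over time appears in both means of each arm and cancels. REML fits of the planned model to simulated data (8 data sets per setting, covariate imbalanced by 0.2 SD) gave:

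- Complete data: adding the covariate changed the estimate by less than 1e-14 and the SE by at most 2e-6.
- About 24% dropout by 12 months, depending on the covariate and the baseline outcome (an assumed mechanism, somewhat heavier than the plan's 20%): the estimate moved by up to 0.015 against a mean SE of 0.081, about 0.2 SE. The SE moved by at most 0.0005.

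**3. Adjusting for the baseline outcome.** For the between-arm difference in means at one time point:

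- Variance V = 2 × (0.02/25 + 0.98/250) = 0.00944.
- Covariance between the baseline and 12-month differences C = 2 × (0.02/25 + 0.58/250) = 0.00624.

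| 12-month contrast | Variance | SE | Power at d = 0.19 |
|---|---|---|---|
| Planned interaction, 2(V − C) | 0.00640 | 0.0800 | Φ(2.375 − 1.96) = 0.66 |
| Baseline-adjusted, V − C²/V | 0.00944 − 0.00412 = 0.00532 | 0.0729 | Φ(2.606 − 1.96) = 0.74 |

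The ratio is 0.00532/0.00640 = 0.83. If the baseline slope is instead the within-facility one, b = 0.58/0.98 = 0.592, the variance is V − 2bC + b²V = 0.00944 − 0.00739 + 0.00331 = 0.00536, ratio 0.84. A textbook check without clustering gives (1 − 0.6²) / (2 × (1 − 0.6)) = 0.64/0.80 = 0.80.

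To match 0.00532 with the planned interaction would take about 500 × 0.00640/0.00532 ≈ 602 evaluable residents. For the mean of both visits, power goes from 0.78 to 0.88. For the 2-df test with d at both visits it goes from 0.69 to 0.80.

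In the simulations, baseline adjustment (fitted as a common baseline mean) gave variance ratios of 0.83 with complete data and 0.87 with dropout. Adding the prognostic covariate to that model lowered them slightly, to 0.82 and 0.85.

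**4. Source of the loss.** Adding covariate-by-time terms to the planned model gave variance ratios of 1.00 to 1.01, so no gain. The loss comes from the free baseline difference. Neither the way covariates are chosen nor their main-effect form causes it.

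**The case against.** The strongest reply is that the planned analysis is a recognised and valid one, and that several harsher readings fail. That is largely right.

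- *A reader might infer that the data alone choose the covariates.* The sentence after the rule names prognostic constructs in advance. Whether they enter unconditionally is unclear, so the defect is ambiguity.
- *A reader might infer that data-driven selection biases the H1 test or inflates its error rate.* For the linear mixed model it hardly can, because the selected main effects cancel from the interaction.
- *A reader might infer that baseline imbalance goes uncorrected.* The interaction is a difference in change, so time-constant level differences between arms are already removed. What main-effect covariates do not address is imbalance in predictors of change.
- *A reader might infer that the covariates do nothing at all.* That is exact only for complete data in the linear mixed model. Under the maximum likelihood analysis with attrition they shift the result slightly, and the Missing data paragraph considers adding baseline covariates to support the missing-at-random assumption.
- *A reader might take 0.66 as disproof of the stated power.* The plan does not name its test, and one reasonable contrast gives 0.78.

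A further objection concerns the remedy. The Setting section randomizes a facility once it expresses interest, and Table 3 lists resident recruitment within the intervention months. If residents enter after allocation, equal expected baselines are not guaranteed, and the baseline-adjusted and change analyses can then disagree. This stands as a caveat, and it is why the planned model should be kept alongside.

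**Conclusion.** The point holds as one of clarity and efficiency. The covariate rule is ambiguous and has almost no effect on the test it is meant to serve: none with complete data, and up to about 0.2 SE under the simulated dropout. Independently of that rule, leaving the baseline outcome unadjusted gives up precision. Adjustment would reduce the 12-month variance by about 17% with complete data (16% with the within-facility slope) and about 13% with dropout, and raise power at d = 0.19 from 0.66 to 0.74.

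These figures rest on the plan's ICC and correlation, a random-intercept covariance with no facility-by-time component, 10 evaluable residents per facility, and an assumed dropout mechanism with few simulated data sets. They apply to the continuous outcomes. The Poisson models for adverse events and the facility-level models were not examined. Nothing here shows bias in the planned analysis.

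**What to change.** In Data Analysis, Effectiveness:

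1. Delete the rule that selects covariates by observed group difference.
2. For continuous resident outcomes, model the 4- and 12-month values with group, time, group-by-time, the resident's baseline value of that outcome, and a fixed covariate list that is included whatever the observed differences. The list would be age, gender, CIRS, BIMS, baseline Barthel where function is not the outcome, state and cohort. The Barthel condition prevents baseline function from entering the function model twice. Keep the facility and resident random effects.
3. Test the adjusted group difference, naming the visit in advance. The Aim 1 research question points to 12 months.
4. Keep the planned group-by-time model, with baseline as a response, as a sensitivity analysis. State whether resident enrolment and baseline assessment precede knowledge of the facility's allocation.
5. State a rule for missing baseline values, which the planned model does not need but a baseline covariate does.

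The cost is SAP wording and a few facility-level degrees of freedom for state and cohort. The resident variables are already collected at baseline, and state and cohort are known by design. Pain is on the plan's list, but the measures text describes it only as a facility-level example; it can be added if the appendices hold a resident-level measure.

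### The Poisson mixed model for falls and transfers does not model window-to-window extra variation, so its 5% group-by-time test can be too liberal: mildly for rare events, substantially for frequent falls

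*Combined protocol and SAP*

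**What the plan says.** Under Resident RE-AIM Measures, "Adverse events will include falls and transfers to hospitals or emergency rooms and physical restraint use". The windows follow: "Baseline will include the four months prior to treatment implementation; 4 month will include those between baseline and 4 months", and the last window runs from month 4 to month 12, so the lengths are 4, 4 and 8 months.

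The Data Analysis section (Aim 1, Effectiveness) assigns "Mixed-effect Poisson regression [i.e., Generalized Linear Mixed Model" to "count outcomes (i.e., number of adverse events including number of falls, hospitalizations and emergency room visits, restraint use". Fixed effects are group, time, group-by-time and covariates. On the rest of the structure it says "Random effects will include facilities and residents". On inference: "The hypothesis will be tested by evaluating the interaction term for each outcome variable", and "All tests will use a 5% significance level".

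On model checking, the section commits to describing the spread of each outcome, to transforming where needed, and to exploring assumptions for each hypothesis. It adds "Post-analysis diagnostic measures (e.g., residuals) will be explored to assess model fit". It names no dispersion parameter, negative binomial model, observation-level effect, facility-by-time effect or robust variance.

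This point covers falls, hospitalizations and emergency room visits. It does not concern restraint use, the summing of event types, or exposure time.

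**The concern.** Each resident contributes three counts. A resident intercept captures the part of that person's event rate that is the same in all three windows, and a facility intercept does the same for the home. Both largely cancel from a group-by-time contrast, which compares windows within residents. What remains is variation within a window: a cluster of falls during an acute illness, or a run of transfers in one period. The Poisson model fixes that variance at the mean. If the true variance is larger, the standard error of the interaction is too small and the test rejects too often.

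At stake is the adverse-event clause of H1. A chance difference could be reported as fewer falls, or as a harm signal, with an interval that is too narrow. The linear mixed models for continuous outcomes estimate a residual variance and do not share this weakness. The sample size is not affected.

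**Working it through.** **Inputs from the documents.** 50 facilities, 25 per arm; 500 analysable residents (625 enrolled, 20% attrition: 625 × 0.80 = 500), so 250 per arm and 10 per facility; windows of 4, 4 and 8 months; 5% test of the interaction (2 df over three windows).

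**Assumptions, because the documents give no figures.** Mean count per 4 months, μ; window-level gamma variance, a; resident log-variance 0.5.

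**The plan's own figure.** The only figure stated for this test is 5%. With no window-level variation (a = 0) it is reproduced: 0.046 to 0.051 in a simulated Poisson random-intercept model (1000 null trials per setting), and 5.2% to 6.0% in a second simulation with 50 facilities of 10 residents (4000 null trials per setting). Stable differences between residents and homes therefore do no harm.

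**Formula.** With complete data, the interaction test depends on total counts by arm and window. For n residents per arm, the within-resident variance of the log total in a window with mean μ_w is (1/n)(1/μ_w + aκ), where κ = exp(0.5) = 1.649. The Poisson model uses only (1/n)(1/μ_w). With means μ, μ and 2μ, the two independent contrasts have variance inflated by 1 + κaμ (4 months against baseline) and 1 + 1.5κaμ (12 months against the other two). With the average multiplier λ = 1 + 1.25κaμ, the rejection rate is approximately exp(−5.991/(2λ)). It depends on a and μ only through their product.

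Example, μ = 0.4 and a = 0.5: λ = 1 + 1.25 × 1.649 × 0.2 = 1.412; exp(−5.991/2.824) = 0.120.

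| μ | a | λ | Formula | Simulation |
|---|---|---|---|---|
| 0.1 | 0.5 | 1.103 | 0.066 | 0.066 |
| 0.1 | 1.0 | 1.206 | 0.083 | 0.081 |
| 0.2 | 0.5 | 1.206 | 0.083 | 0.081 |
| 0.2 | 1.0 | 1.412 | 0.120 | 0.121 |
| 0.4 | 0.5 | 1.412 | 0.120 | 0.129 |
| 0.4 | 1.0 | 1.825 | 0.194 | 0.201 |
| 0.8 | 0.5 | 1.825 | 0.194 | 0.185 |
| 0.8 | 1.0 | 2.649 | 0.323 | 0.332 |

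The rows for μ = 0.1 and 0.2 come from the second simulation (resident gamma variance 0.5, facility log-variance 0.1). The others come from the fitted random-intercept model.

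At a = 0.1 to 0.25 with μ = 0.4 to 0.8, the product runs from 0.04 to 0.20 and the formula gives 0.063 to 0.120. At μ = 0.05 and a = 0.5 it gives 0.058.

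**12-month contrast alone.** The variance ratio is 1 + (4/3)κaμ. At aμ = 0.2 this is 1.44, so the standard error is understated by 1 − 1/√1.44 = 17% and the size is 2Φ(−1.96/1.20) = 0.10. At aμ = 0.8 the ratio is 2.76, the understatement 40% and the size 0.24.

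**Both intercepts and dropout.** A Poisson model with facility and resident intercepts, 12 residents per facility and 20% dropout, at μ = 0.5, rejected 4.0%, 10.5% and 22.6% of null trials for a = 0, 0.5 and 1.0 (124 trials each; Monte Carlo error about 2 to 4 points).

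**Variation shared within a facility.** A facility-by-window log-variance s² adds s²/25 per window and arm, against a Poisson term of 1/(250μ), so 10s² takes the place of aκ. At s² = 0.05, λ = 1 + 1.25 × 0.5 × 0.4 = 1.25 gives 0.091, and μ = 0.8 gives λ = 1.50 and 0.136. Simulation gave 0.09 to 0.15. Over s² = 0.02 to 0.10 and μ = 0.2 to 1.0 the simulated range was 5.6% to 30.3%.

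**Remedies.** A negative binomial mixed model gave 0.060 (μ = 0.4, a = 0.5) and 0.038 (μ = 0.8, a = 1.0), on data with independent resident-level noise only (400 trials each). Facility-clustered robust variance with an F(2,47) reference gave 4.7% to 6.5% in all scenarios, including shared facility-by-window variation.

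**The case against.** A reader might infer that every adverse-event test in this trial will reject several times too often. The documents do not support that. They give neither rates nor dispersion, and at small extra variation or low rates the excess is slight. If transfers are rare, their test may be only a little above 5%.

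A reader might also infer that the plan ignores overdispersion. It does not: it commits to looking at spread, assumptions and residuals, and the error rates above assume that nobody acts on what those checks show. What stands is narrower. There is no criterion and no named replacement, so the choice of model would be made after the data are seen. Transformation does not repair a Poisson variance. The flexibility claimed in the same section concerns the residual covariance of the linear mixed models, which a Poisson model lacks.

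The assumed noise can also be questioned. Short episodes should partly average out over the 8-month window. Halving the variance there lowers the 2-df error to 0.11 and 0.16 (mean 0.4) and 0.16 and 0.27 (mean 0.8), which is smaller but still well above 0.05.

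Finally, it is tempting to treat a negative binomial model as a full cure. It is not. Its dispersion is independent across residents, so with 10 residents per facility it absorbs only about a tenth of the excess variance shared within a home. This objection stands and shapes the fix.

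**Conclusion.** The concern holds in direction; its size is conditional. The specified model has no term for variation that changes from window to window, and the test it feeds depends on that variation. For 500 residents the true size of the nominal 5% test is about 0.05 with no or little such variation. It is about 0.06 to 0.10 over most of the range for rare counts (mean 0.05 to 0.2 per 4 months, variance 0.5 to 1.0), reaching 0.12 at the top corner of that range. It is about 0.12 to 0.33 for frequent falls (mean 0.4 to 0.8, same variances). Means, variances and the resident log-variance of 0.5 are assumptions. The point is confined to the count outcomes in one of the five clauses of H1. It is worth changing because the change is cheap and can be made before any data are seen.

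**What to change.** In the Data Analysis section (Aim 1, Effectiveness), for falls, hospitalizations and emergency room visits:

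- replace the Poisson mixed model with a negative binomial mixed model, or a Poisson model with an observation-level random effect;
- keep the facility and resident random effects;
- add a facility-by-time random effect, or facility-clustered robust variance with a small-sample reference distribution, to cover variation shared within a home.

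The negative binomial model and the robust variance were each simulated separately. The observation-level effect, the facility-by-time effect and the combination were not, so a short null simulation of the final choice would be sensible.

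The cost is a few lines of text and model options, and somewhat wider intervals on the event rate ratios. Recruitment, data collection and sample size are unchanged. If there is no extra variation, the negative binomial model reduces to Poisson and little is lost.
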